12.2. General Statistical Methods

12.2.1. Analysis Sets

The Intent-to-Treat (ITT) subject population includes all subjects who provide written informed consent to be enrolled into the study and have a surgery initiated (i.e. incision in vagina) regardless of their adherence with the entry criteria, regardless of treatment and withdrawal/protocol deviations.

The treated population includes all subjects who undergo a study surgical procedure. The subject is defined to have successfully completed the surgical procedure (i.e. prolapse repair successful) and discharged.

The Per Protocol (PP) population includes all subjects in the ITT Population who received the assigned treatment and had no major protocol deviations.

All primary and secondary endpoints will be analyzed on the ITT Population. The primary safety endpoint and non-safety endpoints will also be analyzed on the per-protocol population.

12.2.2. Control of Systematic Error/Bias

To reduce selection bias in this non-randomized study, each study center will be permitted to enroll subjects in only one of the treatment groups. Physicians will be selected based on device and clinical research experience and the decision as to which device to implant in subjects prior to study initiation at each center. Some study centers may be permitted per Boston Scientific to enroll subjects in both treatment and control groups. All decisions will be documented prior to subject enrollment. All subjects meeting the eligibility criteria at the study center will be screened and enrolled as applicable.

Propensity score stratification will be utilized to address the potential imbalance in risk factors between groups, described in Section 12.2.3 (Propensity Score Methodology). This analysis will be performed blind to all clinical outcome data and prior to performing any analysis of endpoints.

12.2.3. Propensity Score Methodology

Analyses comparing the treatment groups will be adjusted for the propensity score. The propensity score is the probability that the subject enrolled in the mesh arm rather than the native tissue (control) arm, given the characteristics of the subject and center. The characteristics identified are as follows: age, race, body mass index, smoking, diabetes, post-menopausal, prior prolapse repair, prior hysterectomy, estrogen use, POP-Q C measurement, POP-Q Ba measurement, POP-Q Bp measurement, concomitant repair for stress urinary incontinence, and surgeon case volume. Logistic regression of both treatment arms (i.e., (transvaginal biologic mesh repair vs. native tissue repair) on these characteristics will be used to estimate the propensity score. The subjects will then be partitioned into five strata corresponding to quintiles of the propensity score. If the balance between treatment arms within the strata is deemed adequate, the treatment difference adjusted for propensity score stratum will be estimated as described in the following.

The propensity adjusted treatment difference will be based on averaging the treatment differences of the propensity score strata. For a binary outcome, the within-stratum treatment difference is $D_j = p_{T_j} - p_{C_j}$, where p_{T_j} and p_{C_j} is the proportion of treatment and control subjects, respectively, in stratum j . The variance of D_j is approximately

$$V_j = \frac{p_{T_j}(1 - p_{T_j})}{n_{T_j}} + \frac{p_{C_j}(1 - p_{C_j})}{n_{C_j}}$$

Denoting the number of subjects in stratum j by $n_j = n_{T_j} + n_{C_j}$, the treatment difference will be estimated by the (weighted) mean of the within-stratum treatment differences

$$D = \sum_j \frac{n_j}{n} D_j$$

where $n = \sum_j n_j$ is the total sample size across all strata and study arms. D is approximately normally distributed with variance

$$V = \sum_j \left(\frac{n_j}{n}\right)^2 V_j$$

from which a confidence interval for the true treatment difference will be constructed. For each continuous outcome, the confidence interval will be constructed similarly, with D and V obtained as above with the treatment difference within each stratum replaced by $D_j = \bar{X}_{T_j} - \bar{X}_{C_j}$, where \bar{X}_{T_j} and \bar{X}_{C_j} , respectively, is the mean of the treatment and control subjects, and

$$V_j = \frac{S_{T_j}^2}{n_{T_j}} + \frac{S_{C_j}^2}{n_{C_j}}$$

where $S_{T_j}^2$ and $S_{C_j}^2$ are the variances of the treatment and control subjects in stratum j .

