7.1. Primary Endpoints

The primary endpoint of the study is to achieve non-inferiority of transvaginal repair with Xenform over native tissue repair at 36 months as compared to baseline.

Success will be based on a composite of objective and subjective measures, and subjects will be considered a surgical success if each of the three criteria is met:

1. Subjective success is achieved if the patient denies symptoms of vaginal bulging per PFDI-20 question 3, answering “no” or “yes” but “Not at all” bothersome (<2).
2. Anatomic success (in the operated compartment):
 - Anterior segment: Leading edge of anterior prolapse is at or above the hymen or POP-Q point Ba \leq 0.
 - Apical segment: The vaginal apex does not descend more than one-half into the vaginal canal (i.e. POP-Q point C < -1/2 TVL) for multi-compartment prolapse or POP-Q point C \leq 0 for single compartment apical prolapse.
3. No retreatment for POP: No additional surgical treatment for POP in the segment(s) of the vagina treated at the index surgery or no pessary use since index surgery (i.e., ‘treated segment’ refers to the target compartments in this study, which are the anterior and apical compartments).

Additionally, a co-primary endpoint of the study is to achieve non-inferiority of transvaginal repair with Xenform to native tissue repair for safety by comparing rates of serious device or serious procedure related complications between baseline and the 36 month time point. Serious injury is defined per 21 CFR 803.3, i.e., life threatening, results in permanent impairment of a body function or permanent damage to a body structure or injury or illness that requires medical or surgical intervention to preclude impairment of a body function or permanent damage to a body structure.

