9.2. Inclusion Criteria

Subjects who meet all of the following criteria may be given consideration for inclusion in this clinical investigation, provided no exclusion criterion (see Section 9.3) is met.

1. Subject is female
2. Subject is ≥ 18 years of age
3. Subject has pelvic organ prolapse with the leading edge at or beyond the hymen. At or beyond the hymen is defined as POP-Q scores of $Ba \geq 0$ (for prolapse of the anterior compartment alone) or $C \geq 0$ (for prolapse of the Apical compartment alone) or $C \geq -1/2$ TVL and $Ba \geq 0$ (for multi-compartment prolapse that includes the anterior and apical compartments)
4. Subject reports of a bothersome bulge they can see or feel per PFDI-20, question 3 response of 2 or higher (i.e. responses of “somewhat”, “moderately”, or “quite a bit”)
5. Subject or subject’s legally authorized representative must be willing to provide written informed consent
6. Subject is willing and able to comply with the follow-up regimen

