11.4.2. Pre-Operative/Baseline Visit

The Pre-operative/Baseline Visit will occur prior to the subject having surgery. The assessments below must be completed prior to study surgery. This visit may be combined

with the Screening/Enrollment Visit and occur up to 3 months prior to surgery with confirmed absence of infection.

- Urine pregnancy test
- Medical history and physical examination: assessment of urinary tract infection (UTI) or other vaginal infection
- Pelvic examination, vaginal length measurement
- Prolapse grading (POP-Q scoring)
- Assess baseline quality of life (PFIQ-7), sexual functioning (PISQ-12), pelvic floor symptoms (PFDI-20)
- Assess baseline level of pain (TOMUS pain scale) and analgesic use
- EQ-5D for health status
- Assessment of risk factors (includes menopausal status, estrogen use, age, smoking, diabetes status, body mass index, hysterectomy status, concomitant procedures, surgeon training and expertise)

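### The propensity score adjusts for baseline anatomy but for no symptom measure, although baseline PFDI-20 question 3 is recorded and is the counterpart of the first effectiveness success criterion

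*Combined protocol and SAP*

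**What the plan says.** Section 12.2.3 lists the propensity covariates as "age, race, body mass index, smoking, diabetes, post-menopausal, prior prolapse repair, prior hysterectomy, estrogen use", then POP-Q points C and Ba, then "POP-Q Bp measurement, concomitant repair for stress urinary incontinence, and surgeon case volume". The list is closed; nothing in its wording marks the items as examples. The subjects are then cut into five strata at the score's quintiles, and section 12.1.1.3 builds the primary confidence interval from those strata. Section 12.2.2 requires the propensity work to be done blind to outcome data and before any endpoint is analyzed.

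PFDI-20 question 3 appears in three other places:

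- Entry (section 9.2): "Subject reports of a bothersome bulge they can see or feel per PFDI-20, question 3 response of 2 or higher".
- Baseline visit (section 11.4.2, also Table 11.1-1): "Assess baseline quality of life (PFIQ-7), sexual functioning (PISQ-12), pelvic floor symptoms (PFDI-20".
- Criterion 1 of the effectiveness composite (section 7.1): "Subjective success is achieved if the patient denies symptoms of vaginal bulging per PFDI-20 question 3".

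**The concern.** The composite has an anatomic criterion and a symptom criterion. Baseline Ba and C, the counterparts of the anatomic criterion, are in the propensity model. The counterpart of the symptom criterion is not, and no reason is given for treating the two differently.

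The study is not randomized. Sites are mostly assigned to one arm (sections 8.2 and 12.2.2), each physician works in one arm only (section 10.1), and part of the control arm may be shared from the PFD Registry (sections 8.1 and 12.3). How bothered women are when they come to surgery could differ between those sources. If it does, and if bother predicts the 36-month composite beyond what the 14 covariates carry, the estimated success difference is biased. In a non-inferiority comparison, bias toward Xenform raises the chance of a false claim, and bias away from it costs power.

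**Working it through.** **1. The plan's own figure.** Inputs from sections 12.1.1.2 and 12.1.1.3: success 70% in both arms, margin 12 points, power 80%, and a two-sided 90% interval, that is, one-sided alpha 0.05.

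n per arm = 2 × p(1−p) × (z0.95 + z0.80)² / Δ² = 2 × 0.21 × (1.645 + 0.842)² / 0.12² = 180.4, so 181. With 20% loss, 181 / 0.80 = 226.25, so 227 per arm and 454 in total. Both figures reproduce. Adding a propensity covariate does not change them.

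**2. The covariate list.** It has 14 entries. Three are anatomic (POP-Q C, Ba, Bp), and none comes from PFDI-20 or any other symptom scale.

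**3. Whether another analysis covers the gap.**

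- The imputation model for the primary endpoint (12.1.1.3) uses treatment arm and success at the post-baseline visits, with no baseline symptom score.
- The multivariable models (12.3.10) may use baseline data but are fitted within each treatment group, so they do not adjust the comparison.
- Change from baseline is used for the quality-of-life scores (12.1.2.3), not for the binary composite.
- Section 12.2.3 makes use of the strata depend on adequate balance, but does not name question 3 as something to check.

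**4. Possible size.** The documents give neither the imbalance nor its link to the composite, so two inputs are assumed: a log-odds of 0.3 for composite failure per question 3 level, given the other covariates, and a residual arm difference of 0 to 0.4 level after stratification.

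- Bias ≈ p(1−p) × 0.3 × difference = 0.21 × 0.3 × difference
- SE = √(2 × 0.21 / 181) = 0.0482, the unstratified SE at 70% in both arms, as in the sample size
- Type I error at the margin, if the bias favors Xenform = Φ(−1.645 + bias / SE)
- Power at equal true rates, if the bias disfavors Xenform = Φ((0.12 − bias) / SE − 1.645)

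| Residual difference (levels) | Bias (points) | Share of margin | Type I error if it favors Xenform | Power if it disfavors Xenform |
|---|---|---|---|---|
| 0 | 0 | 0% | 5.0% | 80% |
| 0.2 | 1.26 | 10.5% | 8.3% | 72% |
| 0.4 | 2.52 | 21% | 13.1% | 63% |

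**The case against.** The strongest reply is that the harm is assumed, and that is correct. Nothing in the documents shows that baseline bother differs by arm or that it predicts the composite; if either is absent, the bias is zero. The upper end is also demanding. If levels 2, 3 and 4 are equally common, the SD is √(2/3) = 0.82, so 0.4 level is about half an SD, left over after stratifying on 14 covariates.

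The design also narrows the route. Entry requires a "question 3 response of 2 or higher" in both arms. Device decisions precede enrollment, and all eligible women at a center are to be screened and enrolled as applicable (section 12.2.2), so a woman's own bother is not meant to choose her arm. These points limit imbalance but do not exclude it. Three response levels remain among eligible women, and case mix can still differ between sites, surgeons and the Registry.

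Three stronger readings are tempting but not supported:

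- *A baseline difference carries over in full to the success difference.* Question 3 is one of three criteria, and the POP-Q terms may absorb part of its effect.
- *The omission makes false non-inferiority more likely.* That holds in one direction only, and the direction is unknown.
- *The safety co-primary endpoint is affected too.* Nothing in the documents links bulge bother to serious device- or procedure-related complications.

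One could also say that any covariate list can be extended. This variable is not an arbitrary addition: it is the already recorded baseline value of an item in the primary endpoint.

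**Conclusion.** The gap is real and confined to the primary effectiveness analysis. The propensity list omits the baseline counterpart of success criterion 1, and no other planned analysis adjusts the arm comparison for it.

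Size and direction are unknown. The bias of 0 to about 2.5 points, the type I error of at most about 13% and the power of about 63% at worst are illustrations. They rest on the assumed log-odds of 0.3 per level and residual difference of 0 to 0.4 level. A reader could reach a larger figure: a 30-point arm difference in the share of highly bothered women, times a 20-point difference in success by bother, gives 0.30 × 0.20 = 6 points, half the margin. The documents support neither input. The case for change rests on its small cost, not on demonstrated bias.

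**What to change.** In section 12.2.3, add baseline PFDI-20 question 3 to the covariate list for the primary effectiveness analysis, and name it in the within-stratum balance check. Use the full recorded score, not only levels 2 to 4: the ITT set in section 12.2.1 keeps subjects whether or not they met the entry criteria, so some may score below 2. Do this in the outcome-blind step that section 12.2.2 already requires.

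Section 12.3.8 plans a propensity-adjusted 12-month analysis, and the documents do not say whether the score has already been fixed for it. If it has, keep that score so that the interim and final models agree. Report question 3 balance within the existing strata. Before the 36-month outcomes are examined, prespecify a sensitivity analysis with question 3 added to the model.

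The cost is one more model term and a wording change or, in the fallback, one balance table and one extra analysis. No new data are needed, and the planned 181 evaluable and 227 enrolled per arm are unchanged.

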The primary endpoint will be assessed once all per protocol subjects have completed the 36 month study visit. All per protocol subjects will be followed to month 36, until study completion, or until discontinuation prior to month 36. All study procedures will be standardized for uniformity. Prior to enrolling a subject, physicians must have completed a minimum of 10 procedures (defined for each arm) in order to document competency and experience. For the native tissue arm, physicians must have completed a minimum of 10 transvaginal anterior-apical prolapse repair procedures that incorporate an apical vault suspension utilizing either a uterosacral ligament suspension or sacrospinous ligament fixation. For the Xenform arm, physicians must have completed a minimum of 10 native

tissue repair procedures (as defined for the native tissue arm) augmented with a biologic graft or Xenform, and the uterosacral and/or sacrospinous ligaments must be accessed via the anterior compartment incision. Physician training, specialty, and site procedure location (such as private-practice, hospital, academic medical center, etc.) will be recorded.

All efforts will be made to ensure all follow-up anatomic measurements (POP-Q) will be assessed by a healthcare provider to reduce surgeon bias on outcomes after the index procedure. In the event the treating surgeon is the only qualified healthcare provider at the site trained in POP-Q assessments, the follow-up anatomic measurements will be performed by the treating surgeon.

All enrolled subjects will have an anterior and/or apical defect. Concomitant procedures to treat a secondary defect can occur (including an anterior repair, posterior repair, hysterectomy, or sling placement for stress urinary incontinence) at the time of prolapse repair for the primary defect, per physician discretion. Sling placement may include a synthetic material yet a concomitant anterior repair or posterior repair cannot include a biologic graft or a synthetic implant. An anterior colporrhaphy may be required, if clinically necessary. All concomitant procedures performed will be recorded.

Subjects who undergo a medical intervention (surgical or non-surgical) to treat recurrence, persistence of POP, or Xenform or suture complication will be followed to month 36 from the initial study procedure.

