8.2.1. Treatment

The treatment device in this study is the Xenform® Soft Tissue Repair Matrix (“Xenform”). Please refer to the Directions for Use document for device-specific information. The Xenform surgical procedure will be standardized across all centers for uniformity through the application of step-by-step instructions for placement. Physicians will be trained to the standardized procedure steps prior to the first study procedure being performed. Minor modifications to the standardization may be necessary based on a physician’s practice and patient care.

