10.1. Point of Enrollment

Subjects will be considered enrolled in the study once an incision is made in the vaginal wall. All enrolled subjects will have been consented and assigned to receive either the treatment or control procedure per site assignment. Per Boston Scientific's discretion, a site may be considered for participation in both the treatment and control procedure arms however each physician must be designated to one arm only. All enrolled subjects with a surgery initiated (i.e. incision in vagina) will be considered part of the Intent-to-Treat (ITT) population for the final study analysis. All ITT subjects who are treated with a study procedure and had no major protocol deviations will be considered part of the Per Protocol analysis.

The following study timeline (see Table 10.1-1) is based on milestones completed and the current follow-up visit cadence.

Table 10.1-1: Study Timeline

Study Milestones	Dates
Final FDA Approved Protocol	September 2013
First Site Initiated or Enrollment Ready	January 2014
Last Site Initiated or Enrollment Ready	December 2014
First Subject Enrolled	February 2014
Last Subject Enrolled	December 2016
Expected Date of Subject Follow-up Complete	December 2019
Expected Date of Final Database Lock/Study Completion	February 2020
Expected Date of Final Report Submission to FDA	June 2020

All efforts will be made by site staff to ensure minimal loss to follow-up of patients and will follow a site-specific loss to follow-up plan. The plan may include efforts such as telephone

follow-up, Investigator-patient counseling, visit reminder tools, patient stipends if permitted per site IRB, and/or other communication methods.

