12.3. Data Analyses

Presentation of summary statistics for continuous variables will include N, mean, median, standard deviation, minimum, and maximum values for non-missing data. For categorical variables, the number and percentage under each category for non-missing data will be presented.

Additionally, subjects meeting this study's eligibility criteria under the PFD Registry may be included in the analyses plan. The intention is to utilize a shared control arm from the PFD Registry.

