19.6. Risk to Benefit Rationale

The use of transvaginally placed mesh has been shown to reduce recurrent prolapse following pelvic floor repair. There have been many randomized controlled trials comparing outcomes for pelvic floor repair procedures using mesh to non-mesh repair. Of those studies, a reduced incidence of recurrent prolapse in the mesh-procedure group has been reported as compared to non-mesh groups.

However, the risk of mesh-related complications has been reported and can be linked to risk factors including body mass index (BMI), concomitant hysterectomy, and physician experience. There is no new literature to indicate there would be an unsatisfactory risk benefit profile for the use of transvaginally placed mesh for the treatment of POP.

20. Informed Consent

Subject participation in this clinical study is voluntary. Informed Consent is required from all subjects or their legally authorized representative. The Investigator is responsible for ensuring that Informed Consent is obtained prior to performing any study-required procedures and/or testing, or data collection.

The obtaining and documentation of Informed Consent must be in accordance with the principles of the Declaration of Helsinki, ISO 14155:2011 (Clinical investigation of medical devices for human subjects - Good clinical practice), any applicable national regulations, and local Ethics Committee and/or Regulatory authority body, as applicable. The ICF must be accepted by Boston Scientific or its designee (e.g., CRO), and approved by the center's IRB/EC, or central IRB, if applicable.

Boston Scientific will provide a study-specific template of the ICF to investigators participating in this study. The ICF template may be modified to meet the requirements of the investigative center's IRB/EC. Any modification requires approval from Boston Scientific or its designee (e.g., CRO) prior to use of the form. The ICF must be in a language understandable to the subject and if needed, BSC will assist the center in obtaining a written consent translation. Translated consent forms must also have IRB/EC approval prior to their use. Privacy language shall be included in the body of the form or as a separate form as applicable.

The process of obtaining Informed Consent shall:

- be conducted by the Principal Investigator or designee authorized to conduct the process,

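### The variance behind the 90% CIs treats all women as independent, although each study surgeon is in one arm and centers are one-arm by default; non-negligible residual clustering makes the non-inferiority tests too lenient

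*Combined protocol and SAP*

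**What the plan says.** Section 12.2.3 estimates the treatment difference D as the average of the differences within five propensity quintiles, weighted by stratum size. Its variance is V = Σ(n_j/n)²V_j, with V_j = pT(1−pT)/nT + pC(1−pC)/nC, "from which a confidence interval for the true treatment difference will be constructed". Section 12.1.1.3 sends both co-primary endpoints to this interval (two-sided 90%, margins −12% and 11.6%), and 12.3.8.2 does the same for the interim tests.

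On allocation, 10.1 allows a site to run both arms but adds that "each physician must be designated to one arm only". Section 12.2.2 sets the default that "each study center will be permitted to enroll subjects in only one of the treatment groups", with an exception: "Some study centers may be permitted per Boston Scientific to enroll subjects in both treatment and control groups". For the registry controls, 12.3 says "The intention is to utilize a shared control arm from the PFD Registry"; no arm rule for registry surgeons is given.

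The only surgeon characteristic in the propensity model is case volume. Section 12.3.9 examines differences between institutions, separately within each group, to support pooling. The sample size in 12.1.1.2 has no ICC or design effect.

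**The concern.** If patients of one surgeon resemble each other in outcome, and each surgeon contributes to one arm, the surgeon's effect goes straight into the arm difference. The same holds for a site that enrolls one arm. The variance of D then has a between-cluster component that binomial terms cannot contain. It also has covariances between strata, because one surgeon's patients can fall in several quintiles. V has neither.

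The documents give reasons to expect some correlation. Where no one else at the site is qualified, "the follow-up anatomic measurements will be performed by the treating surgeon" (section 8), and POP-Q feeds the anatomic component of the primary composite. For the Xenform steps, "Minor modifications to the standardization may be necessary" to suit a physician's practice (8.2.1). Mesh complications "can be linked to risk factors including body mass index (BMI), concomitant hysterectomy, and physician experience" (19.6).

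At stake is the error that a non-inferiority study most needs to control: concluding that Xenform is acceptable when it is worse by the full margin. By their footnotes, the interim analyses also support a premarket application.

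**Working it through.** **Inputs from the documents.** Success 70% (taken equal in both arms), margin 12%, one-sided 0.05, power 80%, 181 per arm. Complications 14%, margin 11.6%, power 90%, 154 per arm. Loss 20%, 227 enrolled per arm (all 12.1.1.2). Up to 40 sites, with 15 to 50 women per site encouraged (8.1).

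**Assumed.** ICC 0.01 to 0.10; in the formula, equal clusters, each wholly in one arm.

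**1. The plan's figures reproduce under independence.**
- Effectiveness: 2 × 0.7 × 0.3 × (1.645 + 0.842)² / 0.12² = 180.4, so 181 per arm; 181/0.8 = 226.25, so 227 per arm and 454 in all.
- Safety: 2 × 0.14 × 0.86 × (1.645 + 1.282)² / 0.116² = 153.3, so 154 per arm.

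**2. Cluster size m.** With all 40 sites, 362/40 = 9.05 evaluable women per site. The 15 to 50 guidance, less 20%, gives 12 to 40 evaluable, so 15 is a second reasonable value. Sites meeting that guidance would number between 454/50 ≈ 9 and 454/15 ≈ 30. If the correlation is at surgeon level with two surgeons per site (an assumption), m is about 5.

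**3. True one-sided error at the margin.** Design effect DE = 1 + (m − 1) × ICC; error = Φ(−1.645/√DE). Example, m = 9.05 and ICC 0.05: DE = 1 + 8.05 × 0.05 = 1.4025; 1.645/1.184 = 1.389; error 8.2%.

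| m | ICC 0.01 | 0.02 | 0.05 | 0.10 |
|---|---|---|---|---|
| 5 | 5.3% | 5.7% | 6.7% | 8.2% |
| 9.05 | 5.7% | 6.3% | 8.2% | 11.0% |
| 15 | 6.2% | 7.3% | 10.4% | 14.4% |

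**4. Simulation of D and V as written in 12.2.3.** 20 single-arm sites per arm, five strata, 20,000 runs, ICC 0 / 0.01 / 0.02 / 0.05 / 0.10.
- Effectiveness, truth 58% against 70%, equal sites: 5.5 / 5.8 / 6.8 / 8.2 / 10.7%.
- Effectiveness, unequal sites (coefficient of variation 0.6): 5.4 / 6.4 / 6.7 / 9.8 / 13.2%.
- Safety, truth 25.6% against 14%, 227 per arm: 5.3 / 6.5 / 6.8 / 9.6 / 12.7%.

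**5. Mixed centers.** With all 40 sites mixed, a site effect shared by the arms leaves the planned error at 5.2 / 5.3 / 5.1 / 4.8 / 4.5% over the same ICCs. Surgeon-level correlation still gives 5.2 / 5.4 / 6.2 / 6.5 / 8.0%.

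**6. Power once the variance is right.** SE = √(0.42/181) = 0.0482; power = Φ(0.12/(SE√DE) − 1.645). At m = 9.05 and ICC 0.01 / 0.02 / 0.05 / 0.10 this is 77 / 75 / 68 / 58%, against 80% at ICC 0.

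**The case against.** **The plan already works against clustering.** Procedures are standardized, surgeons are trained and have at least 10 prior cases, someone other than the surgeon is to measure POP-Q where possible, the permitted modifications are minor, and case volume is in the score. The complication statement in 19.6 does not concern composite success. All of this stands as a reason to expect a modest ICC. None of it puts what remains into V, and 12.3.9 has no rule that alters the CI if institutions differ.

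**V can err in the other direction.** A reader might infer that any positive correlation must push the error above 5%. That is too strong. Stratifying on an estimated score that contains prognostic covariates tends to make the binomial V too large. Simulations used a fitted score (13 patient covariates plus surgeon volume), 20 single-arm sites per arm and 10,000 runs, with covariate strength assumed. The planned error at ICC of about 0 / 0.01 / 0.02 was 4.9 / 5.6 / 6.3% when covariates explained 10% of latent outcome variance, 4.3 / 5.2 / 5.4% at 20%, and 3.9 / 4.5 / 5.2% at 30%. At ICC 0.05 it was still 7 to 8%. So the offset can absorb a small ICC but did not absorb a larger one.

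**A simple sandwich variance is not a safe replacement.** With a G/(G−2) multiplier and t on G−2 df (G sites), its error was 6.6% at ICC 0, against 5.1% as planned, when surgeon volume was shifted between arms by an assumed 0.8 SD. With 10 sites per arm and no shift it was 6.0 to 6.7%. This objection stands and shapes the fix.

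**Conclusion.** The point holds with conditions. The independence assumption is in the formula, the one-arm rule for surgeons is in the text, and nothing joins the two. Where residual correlation within surgeon or single-arm site is not negligible, the 90% CIs are too narrow and the error at the margin exceeds 5%. The excess is small, and possibly nil, at ICC of about 0.02 or less, and material from about 0.05. The documents do not give the ICC, the number of surgeons per site, or the clustering of registry controls, so the size is a range and not an estimate.

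Two further inferences are not supported. One is that non-inferiority would be declared more often whatever the truth: with truly equal arms, the planned rule declared it less often in simulation (80% at ICC 0, 73% at ICC 0.10). The other is that all site effects bias the interval: at mixed centers, an effect common to both arms largely cancels.

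This should be fixed, because the decision rests on this error bar and the remedy is cheap.

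**What to change.** - **12.2.3:** keep D. Base the primary effectiveness, primary safety and interim CIs on a prespecified cluster-robust variance with study site as the cluster. Both arms of a mixed center form one cluster, surgeons are nested in their site, and registry controls are clustered by registry site. Use a small-sample correction suited to roughly 10 to 40 unequal clusters, for example a CR2-type bias-reduced variance with Satterthwaite df. That form was not simulated here, so its error should be checked on the actual site layout, blind to outcome.
- **Effectiveness, including its interim version:** compute the variance in each imputed data set and combine by Rubin's rules.
- **12.2.2:** fix cluster level and method at the outcome-blind propensity step. Report the independent-subject V as a sensitivity analysis.
- **12.1.1.2:** state that 181 per arm and 80% power assume independent subjects, and give the clustered power at 9 women per site over the ICC range.

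**Cost.** SAP wording, modest programming and a site identifier for registry controls; N stays at 454. The CI widens and the stated power falls. At ICC 0 the loss is about 1 point (79.1% against 80.4%, simulated with the simple sandwich form).
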